#### Assessment of Causality (related to transfusion/study intervention)

Definite (certain): when there is conclusive evidence beyond reasonable doubt that the

adverse event can be attributed to the transfusion

**Probable (likely**): when the evidence is clearly in favor of attributing the adverse event to the transfusion

**Possible:** when the evidence is indeterminate for attributing the adverse event to

the transfusion or an alternate cause

Unlikely (doubtful): when the evidence is clearly in favor of attributing the adverse event

to causes other than the transfusion

**Excluded**: when there is conclusive evidence beyond reasonable doubt that the adverse event can be attributed to causes other than the transfusion

# 10.4. Appendix 4: Definitions of SAE of special interest (transfusion reactions)

#### Transfusion reactions

Immunological:

- Transfusion-related acute lung injury (TRALI)
- Acute hemolytic transfusion reaction (AHTR)
- Anaphylactic reaction
- Other

Non- immunological:

- Transfusion transmitted infection (bacteria, virus, parasites)
- Transfusion associated circulatory overload (TACO)
- Hypotensive transfusion reaction
- Other

#### **Transfusion reactions-Definitions**

## TRALI (Transfusion associated acute lung injury)

In patients with no evidence of acute lung injury (ALI) prior to transfusion, TRALI is

diagnosed if a new ALI is present (all five criteria should be met):

- Acute onset
- Hypoxemia
- $o Pa0_2 / Fi0_2 < 300 mm Hg or$
- o Oxygen saturation is < 90% on room air or

o Other clinical evidence

Bilateral infiltrates on frontal chest radiograph

No evidence of left atrial hypertension (i.e. circulatory overload)

No temporal relationship to an alternative risk factor for ALI,

during or within 6 hours of completion of transfusion.

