## 5. Study Population

The target population for this study is individuals above the age of 50 in early stages of COVID-19 disease. Participants will be recruited from municipal healthcare institutions that admit and care for symptomatic COVID-19 patients in need of medical care but not referred to hospitals.

In Norway, around 15% of the population is aged 67 years or more. In 2018, around 32200 persons were living in care homes for the elderly on long term basis, and an additional 9000 persons on time-limited stays.

Data on COVID-19 in Norway showed that at end of April 2020, among the total 204 deaths in the population reported, 60% were among patients in institutions outside hospitals, and 89% of the total 204 deaths were persons aged 70 years or more (FHI.no).

The population in care homes has a high proportion of dementia and co-morbidities, which both are significant factors to take into account in the study implementation and outcome analysis. In particular, the presence of dementia represents a challenge for the consent to participate which will need to be handled by the patient's guardian if such is appointed, acting in the best interest of the patient.

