# 8.3.5. Disease-Related Events and/or Disease-Related Outcomes Not Qualifying as AEs or SAEs

The following disease-related events (DREs) are common in participants with COVID-19 and can be serious/life threatening:

- Fever and/or chills
- Need for increased oxygenation or ventilation support
- Persistent pain or pressure in the chest
- New-onset confusion
- Multiple organ dysfunction or failure

Because these events are typically associated with the disease under study, they will not be reported according to the standard process for expedited reporting of SAEs even though the event may meet the definition of an SAE. These DREs will be followed by the medical monitor and recorded by the site designee for later evaluation by the Data Monitoring Committee (DMC).

NOTE: However, if either of the following conditions applies, then the event must be recorded and reported as an AE/SAE (instead of a DRE):

The event is, in the investigator's opinion, of greater intensity, frequency, or duration than expected for the individual participant.

OR

The investigator considers that there is a reasonable possibility that the event was related to study intervention.

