## Transfusion associated circulatory overload (TACO)

TACO is characterized by any 4 of the following:

- Acute respiratory distress
- Tachycardia
- Increased blood pressure
- Acute or worsening pulmonary edema on frontal chest radiograph
- Evidence of positive fluid balance

Occurring within 6 hours of completion of transfusion. An elevated BNP is supportive of TACO.

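### Appendix 4 has no tier for suspected TRALI or TACO, so TRALI, and to a lesser degree TACO, is likely to be under-counted in care-home patients who all have COVID-19

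*Protocol*

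**What the plan says.** Protocol Section 8.3.6 defines AESIs as the transfusion reactions in Appendix 4 (Section 10.4) and sends them to the national haemovigilance system.

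The TRALI entry begins "In patients with no evidence of acute lung injury (ALI) prior to transfusion, TRALI is" and continues "diagnosed if a new ALI is present (all five criteria should be met". The five criteria are acute onset, hypoxaemia, "Bilateral infiltrates on frontal chest radiograph", no sign of left atrial hypertension, and "No temporal relationship to an alternative risk factor for ALI". The time window is "during or within 6 hours of completion of transfusion". The entry has no lower tier, and no rule for a missing radiograph or a competing cause.

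For transfusion-associated circulatory overload the appendix says "TACO is characterized by any 4 of the following" and lists five signs, one of them radiographic, with the same 6-hour window.

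Section 8.3.5 lists "Need for increased oxygenation or ventilation support" among the disease-related events, which stay outside expedited SAE reporting. Two exceptions return an event to AE/SAE reporting: it is worse than expected for that participant, or the investigator sees a reasonable possibility that plasma caused it.

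Section 5 describes the population as "symptomatic COVID-19 patients in need of medical care but not referred to hospitals".

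**The concern.** The definitions suit a setting where imaging is routine and most patients have no competing cause of lung injury. In this trial every participant has a respiratory infection, and imaging is not part of the plan. A rule that needs every criterion, with nothing beneath it, tends to push real or suspected reactions out of the named category.

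The label matters because it decides the route. AESIs go to haemovigilance (Section 8.3.6), and any AESI is listed among the events that could contribute to pausing or stopping the study (Section 10.1.4). A respiratory event filed as disease-related does not take those routes as a transfusion reaction. The trial's title names safety, and the risk table in Section 2.3 notes a higher risk of transfusion complications in the elderly. A TRALI count held down by its definition would be weak evidence of safety.

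**Working it through.** There is no stated figure to reproduce. The check sets the definition against the rest of the protocol.

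1. **Alternative risk factor.** Section 5.1 requires a positive PCR within 3 days and symptom onset within 7 days before the intervention. Section 2.2 describes the infection as able to cause serious respiratory illness, and Section 8.3.5 treats rising oxygen need as typical of it. A site that applies the fifth criterion can readily take COVID-19 as a temporally related alternative. The limit to patients without prior lung injury is a separate condition and does not settle this.

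2. **Radiograph.** The schedule (Section 1.2) and the laboratory panel (Appendix 2) contain no chest radiograph. Section 2.2 says care-home patients are not prioritised for advanced supportive treatment. Hypoxaemia may be shown by other clinical evidence, but the imaging criterion has no substitute.

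3. **TACO.** At least four of five signs qualify.
   - Qualifying patterns with imaging available: C(5,4) + C(5,5) = 5 + 1 = 6.
   - Qualifying patterns without the radiographic sign: C(4,4) = 1.

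   Without a radiograph, respiratory distress, tachycardia, raised blood pressure and positive fluid balance must all be present. The schedule has no entry for fluid balance. TACO can still be met, but by one pattern instead of six.

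4. **Detection.** Section 6.1 sets close monitoring for 1 hour, with blood pressure, pulse, respiratory frequency and temperature. Oxygen saturation is not in that list. The TRALI and TACO windows run to 6 hours.

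5. **Contrast within the appendix.** The entry on acute haemolytic reactions accepts that not every feature appears in every case. TRALI has no such allowance.

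6. **Worked case.** A participant becomes hypoxaemic 3 hours after plasma and no radiograph is taken. TRALI fails on imaging, and perhaps also on the alternative-cause criterion. TACO needs all four other signs. The event fits the disease-related item on oxygen need and stays there unless one of the two exceptions in Section 8.3.5 is invoked. If it is invoked, the event becomes an AE or SAE, but the text does not say that it becomes an AESI.

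**The case against.** The strongest reply is that the event is not lost; at most its label changes.

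- Appendix 4 lists 'Other' under both the immunological and the non-immunological reactions, and Section 8.3.6 makes these AESIs. A suspected case can enter there.
- Section 8.3.5 requires AE/SAE reporting when relation to plasma is reasonably possible, and hypoxaemia a few hours after transfusion is an obvious candidate.
- Disease-related events are recorded for the DMC, which reviews all safety data (Section 9.4). Section 6.1 also has serious events under Section 8.3.5 reported immediately to the medical monitor.
- Imaging that is not scheduled may still be done. Appendix 2 allows additional tests when the investigator needs them, and Appendix 3 names radiological scans and foresees hospital and intensive-care transfer. Section 8.2 says delayed events will be registered.
- COVID-19 is not named as an alternative risk factor, and the criterion is a case-by-case judgement of timing.

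All of this stands, and it defeats three stronger readings that a reader might infer: that no participant can ever meet the TRALI definition, that TRALI will necessarily be reported as absent, and that the DMC and the haemovigilance system will not see the events.

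It does not remove the narrower point. 'Other' is undefined and adds nothing to a TRALI count. The relatedness exception rests on an unblinded investigator's judgement, with a definition that points away from TRALI. The DMC may receive the event without its being identified as a possible transfusion reaction.

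**Conclusion.** The concern holds in a limited form. Participants will rarely meet the TRALI definition, so TRALI counts, and to a lesser degree TACO counts, are likely to be too low. Acute respiratory events after plasma may be filed as disease-related, and so may not be identified as transfusion reactions or reported promptly.

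The direction is clear but the size cannot be computed. The protocol gives no expected rate of TRALI or TACO, and nothing in it says that a TRALI rate with a confidence interval will be reported. A count of missed events would therefore rest on an assumed rate.

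The conclusion assumes that sites often regard COVID-19 as a competing cause and that radiographs are seldom taken within the window. If sites judge otherwise, the under-count shrinks.

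The importance is moderate. Incidence of adverse events is listed as an exploratory endpoint, and the primary endpoint, its analysis and the interim rule are unaffected.

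**What to change.** Amend the wording in two places.

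1. **Appendix 4.** Keep the five-criterion TRALI definition as the definite tier. Add an AESI category 'possible TRALI/TACO' for new or worsening hypoxaemia or respiratory distress during transfusion or within the 6-hour window already stated. It applies whether or not a radiograph exists and whether or not COVID-19 is a competing cause. Grade relatedness on the causality scale in Appendix 3, whose 'Possible' level already covers indeterminate evidence.

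2. **Section 8.3.5.** State that events in this window are recorded and reported as AE, SAE or AESI, and not only as disease-related events. Align the sentence in Section 6.1 on serious events under Section 8.3.5 with this.

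Report definite and possible counts separately.

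The cost is a wording amendment and one extra CRF category, with no new procedure. The downside is that some deterioration due to COVID-19 will be counted as possible TRALI/TACO; the causality grade and the separate counts keep that visible.

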## Hemolytic transfusion reaction

A hemolytic transfusion reaction is one in which symptoms and clinical or laboratory signs of increased red cell destruction are produced by transfusion. Hemolysis can occur intravascularly or extravascularly and can be immediate (acute) or delayed.

## Acute hemolytic transfusion reaction (AHTR)

An AHTR has its onset within 24 hours of a transfusion. Clinical or laboratory features of hemolysis are present.

Common signs of AHTR are:

- Fever
- Chills/rigors
- Facial flushing
- Chest pain
- Abdominal pain
- Back/flank pain
- Nausea/vomiting
- Diarrhea
- Hypotension
- Pallor
- Jaundice
- Oligoanuria
- Diffuse bleeding
- Dark urine
- Common laboratory features are:
- Hemoglobinemia
- Hemoglobinuria
- Decreased serum haptoglobin
- Unconjugated hyperbilirubinemia
- Increased LDH an AST levels
- Decreased hemoglobin levels

Not all clinical or laboratory features are present in cases of AHTR.

Blood group serology usually shows abnormal results but absence of immunological findings does not exclude AHTR. AHTR may also be due to erythrocyte auto-antibodies in the recipient or to non immunological factors like mechanical factors inducing hemolysis (malfunction of a pump, of a blood warmer, use of hypotonic solutions, etc.).

#### **Anaphylactic reaction**

An allergic reaction can involve respiratory and/or cardiovascular systems and present as an anaphylactic reaction.

There is anaphylaxis when, in addition to mucocutaneous systems there is airway compromise or severe hypotension requiring vasopressor treatment (or associated symptoms like hypotonia, syncope). The respiratory signs and symptoms may be laryngeal (tightness in the throat, dysphagia, dysphonia, hoarseness, stridor) or pulmonary (dyspnea, cough, wheezing/bronchospasm, hypoxemia).

Such a reaction usually occurs during or very shortly after transfusion.

## Transfusion transmitted infection (bacteria, virus, parasites)

Confirmed by microbiological analyses

## Transfusion associated circulatory overload (TACO)

TACO is characterized by any 4 of the following:

- Acute respiratory distress
- Tachycardia
- Increased blood pressure
- Acute or worsening pulmonary edema on frontal chest radiograph
- Evidence of positive fluid balance

Occurring within 6 hours of completion of transfusion. An elevated BNP is supportive of TACO.

## Hypotensive transfusion reaction

This reaction is characterized by hypotension defined as a drop in systolic blood pressure of  $\geq$ h30 mm Hg occurring during or within one hour of completing transfusion **and** a systolic blood pressure  $\leq$  80 mm Hg. Most reactions do occur very rapidly after the start of the transfusion (within minutes). This reaction responds rapidly to cessation of transfusion and supportive treatment. This type of reaction appears to occur more frequently in patients on ACE inhibitors. Hypotension is usually the sole manifestation but facial flushing and gastrointestinal symptoms may occur.

All other categories of adverse reactions presenting with hypotension, especially allergic reactions, must be excluded. The underlying condition of the patient must also be evaluated as a possible explanation for the hypotension.

